IVRS: Interactive Voice Response Service
LBBB: Left Bundle Branch Block
LGE: Late Gadolinium Enhancement
LV: Left Ventricle
LVESV: Left Ventricular End Systolic Volume
LVSD: Left ventricular Systolic Dysfunction

MHRA: Medicines and Healthcare Regulatory Authority
MI: Myocardial Infarction
MMPs: matrix metalloproteinases
MR: Magnetic Resonance
MRA: Mineralocorticoid Receptor Antagonist
MREC: Medical Research Ethics Committee
NEP: Neprilysin
NSAIDs: Non-steroidal anti-inflammatory drugs
NSTEMI: Non ST Elevation Myocardial Infarction
NT-proBNP: N-Terminal pro BNP
NYHA: New York Heart Association
PGA: Patient Global Assessment
PICP: carboxy-terminal propeptide of type I procollagen
PIIINP: amino-terminal propeptide of type III procollagen
PV: Pharmacovigilance
QEUh: Queen Elizabeth University Hospital
RAAS: Renin Angiotensin Aldosterone System
RAH: Royal Alexandra Hospital
REC: Research Ethics Committee
SAE: Serious Adverse Event
SAR: Serious Adverse Reaction
SBP: Systolic Blood Pressure
SDV: Source Data Verification
SmPC: Summary of Product Characteristics
STEMI: ST Elevation Myocardial Infarction
SUSAR: Suspected Unexpected Serious Adverse Reaction
TIMP: Tissue Inhibitors of Metalloproteinases
TMG: Trial Management Group
TSC: Trial Steering Committee
TTE: Transthoracic Echocardiogram
U&Es: Urea and Electrolytes
ULN: Upper Limit of Normal range
WoCBP: Women of Child Bearing Potential

[figure not shown]
Study Synopsis

Title of study	The effects of sacubitril/valsartan compared to valsartan on left ventricular remodelling in asymptomatic left ventricular systolic dysfunction after myocardial infarction: a randomised, double-blinded, active-comparator, cardiac-MR based trial
Short title	RECOVER-LV
Study centre	Queen Elizabeth University Hospital Clinical Research Facility
Primary endpoint	Change in indexed left ventricular end-systolic volume (LVESVI), from baseline to 12 months (+/- 3months) measured using cardiac MR.
Secondary endpoints	
 Changes in other CMR based metrics of LV remodeling (LVEDVI, LVEF, LV mass index) from baseline to 12 months(+/- 3months) Changes in hsTnI from baseline to 12 months (+/- 3months) Changes in NT-proBNP from baseline to 12 months (+/- 3months) Change in patient well-being as assessed by a patient global assessment questionnaire.
Tertiary endpoints	
 Changes in biomarkers of LV remodelling (sST2, Galectin 3, TIMP-1, MMP-9, Type III Procollagen Peptide and GDF-15) from baseline to 12 months(+/- 3months) Changes in neurohormonal levels (BNP, MR-proANP, C-terminal ANP, CNP, MR-proADM, cGMP, endothelin-1, neprilysin antigen, renin and aldosterone) from baseline to 12 months (+/- 3months)
Rationale	
Prior to reperfusion therapy, the major therapeutic breakthrough in myocardial infarction was the demonstration that ACE inhibitors or ARBs, given to prevent adverse “remodelling” (progressive dilatation and decline in systolic function) in high risk patients, reduced the likelihood of developing heart failure and the risk of death. The neurohumoral systems which are activated in patients after myocardial infarction (and in heart failure) are not all harmful and some endogenous systems may be protective. The best recognised of these is the natriuretic peptide system. A- and B-type natriuretic peptides are secreted by the heart when it is stressed and these peptides promote vasodilation (reducing left ventricular wall stress), stimulate renal sodium and water excretion (i.e. antagonising the retention of salt and water characterising heart failure) and inhibit pathological growth i.e. hypertrophy and fibrosis (key components of the adverse left ventricular remodelling that occurs after infarction and in heart failure). The augmentation of plasma levels of endogenous natriuretic peptides can be achieved through inhibition of neutral endopeptidase, also known as neprilysin (NEP), which is responsible for the breakdown of natriuretic peptides. Recently, the addition of neprilysin inhibition to blockade of the RAAS (using sacubitril/valsartan), compared with RAAS blockade alone, reduced the risk of heart failure hospitalisation and death in patients with HF-REF. These exciting findings may lead to a new approach to the treatment of heart failure, with an angiotensin receptor neprilysin inhibitor (ARNI) replacing an ACE inhibitor as one of the fundamental treatments for this condition. We believe that the same approach may be beneficial in high-risk survivors of myocardial infarction. Recently, sacubitril/valsartan was shown to ameliorate adverse left ventricular remodelling in an experimental model of acute myocardial infarction. The objective of the present proposal is to gather “proof-of-concept”, mechanistic, evidence in humans to support adoption of this new approach in patients at high risk after myocardial infarction as a result of residual left ventricular systolic dysfunction.

Methodology	Prospective, randomised, active-comparator, double-blinded study.

Sample size	100
Screening	Patients with EF ≤40% measured by trans-thoracic echocardiography post myocardial infarction without evidence of clinical heart failure.
Inclusion criteria	
 • Acute myocardial infarction (AMI) at least 3 months prior to recruitment • Left ventricular ejection ≤40% as measured by transthoracic echocardiography • Ability to provide written, informed consent • Age ≥18 years • Tolerance of a minimum dose of ACE inhibitor/ARB (ramipril 2.5mg BD or equivalent) • Treatment with a beta-blocker unless not tolerated or contraindicated.
Exclusion criteria	
 • Contraindication to CMR (ferrous prosthesis, implantable cardiac device or severe claustrophobia) • Clinical and/or radiological heart failure (NYHA≥2) • Symptomatic hypotension and/or systolic blood pressure <100mmHg • eGFR < 30 mL/min/1.73m² and/or serum potassium >5.2mmol/L • Persistent/permanent atrial fibrillation • History of AMI within last 3 months • History of hypersensitivity or allergy to ACE-inhibitors/ARB • History of angioedema • Known hypersensitivity to the active study drug substances, contrast media or any of the excipients • Obesity (where body girth exceeds MRI scanner diameter) • Pregnancy, planning pregnancy, or breast feeding • Inability to give informed consent or comply with study protocol • Evidence of hepatic disease as determined by any one of the following: AST or ALT values exceeding 2 x ULN at Visit 1, history of hepatic encephalopathy, history of oesophageal varices, or history of portacaval shunt • History of biliary cirrhosis and cholestasis • Active treatment with cholestyramine or colestipol resins • Active treatment with lithium or direct renin inhibitor • Participation in another intervention study involving a drug or device within the past 90 days (co-enrolment in observational studies is permitted)
Study drugs	
Patients will be randomised in a 1:1 fashion to sacubitril/valsartan (target dose 97mg/103mg BD) or valsartan (target dose 160mg BD) with matched placebo.
 
 • Sacubitril/valsartan: 24mg/26mg (dose level 1), 49mg/51mg (dose level 2) and 97mg/103mg (dose level 3) twice daily. • Valsartan: 40mg (dose level 1), 80mg (dose level 2) and 160mg (dose level 3) twice daily.
Duration of treatment:	12 months (+/- 3months)
Statistical analysis	The primary outcome will be compared between randomised groups using a linear regression model adjusted for baseline LVESVI value, and whether or not taking diuretics at baseline. Similar methods will be used for other outcomes. The Robertson Centre for Biostatistics will manage and analyse trial data. All statistical analyses will be conducted according to a Statistical Analysis Plan, which will be authored by the Trial Statistician and agreed by the Trial Steering Committee prior to unblinding of randomised groups.

Study Flow Chart

Version 6.0 – In response to COVID-19 the treatment time and study window for the week 52 visit have been altered (+/- 3 months) in order to be able to obtain the primary outcome for this clinical trial and ensure patient participation has been worthwhile

1 Introduction

1.1 Background

The widespread adoption of coronary reperfusion therapy (initially with thrombolysis and latterly with percutaneous intervention) has reduced the extent of left ventricular damage sustained during acute myocardial infarction and the lives lost due to this condition.¹⁻³ Unfortunately, however, LVSD and HF remain relatively common among survivors of myocardial infarction.⁴ A Norwegian nation-wide cohort study between 2001-2009 in 63 583 patients with a first presentation of MI reported that 12.6% of patients were hospitalised or died because of HF over a median follow-up of 3.2 years.⁵ This is because a large proportion of patients are not eligible for reperfusion therapy (i.e. those with non ST-segment elevation myocardial infarction) and many patients suffer recurrent episodes of infarction, leading to cumulative left ventricular damage over time.

Prior to reperfusion therapy, the major therapeutic breakthrough in myocardial infarction was the demonstration that angiotensin converting enzyme (ACE) inhibitors, given to prevent adverse “remodelling” (progressive dilatation and decline in systolic function) in high risk patients, reduced the likelihood of developing heart failure and the risk of death.⁶ These benefits were seen in three seminal trials - Survival And Ventricular Enlargement (SAVE, with captopril), Acute Infarction Ramipril Efficacy (AIRE) and TRAndolapril Cardiac Evaluation Study (TRACE).⁶⁻⁸ In the Valsartan in Acute Myocardial Infarction Trial (VALIANT), the angiotensin receptor blocker (ARB) valsartan was shown to be as effective as captopril used at the same dose as in SAVE.⁹ ACE inhibitors and ARB work by interrupting one of the neurohumoral systems activated in patients who have sustained ventricular injury after infarction (the renin-angiotensin-aldosterone system or RAAS) and their benefits in high-risk myocardial infarction patients parallel similar benefits in patients with chronic heart failure due to left ventricular systolic dysfunction or reduced ejection fraction (HF-REF).¹⁰⁻¹² Indeed, four different neurohumoral antagonists (ACE inhibitors or angiotensin receptor blockers, beta-blockers and mineralocorticoid receptor antagonists) are life-saving in both conditions.⁶⁻¹⁹ This is perhaps not surprising in that one of the commonest reasons patients develop chronic HF-REF is because of myocardial infarction weeks, months, years or decades previously. Many patients progress through an asymptomatic phase of progressive left ventricular remodelling and neurohumoral activation after myocardial infarction before developing symptomatic HF-REF. Another seminal trial showed that identification and treatment of patients with asymptomatic LVSD with an ACE inhibitor may delay or prevent the development of symptomatic HF-REF.²⁰ That trial was the prevention arm of the Studies of Left Ventricular Dysfunction (SOLVD-P), the sister study of SOLVD-T which demonstrated the benefit of the ACE inhibitor enalapril in a broad spectrum of patients with symptomatic HF-REF. As has been said (using old-fashioned terminology), there is a continuum “from the coronary care unit (CCU) to congestive cardiac failure (CCF)” and ACE inhibitors are beneficial across this continuum. The earliest indication of the potential benefit of ACE inhibitors or ARB in high-risk survivors of myocardial infarction was their ability to attenuate adverse left ventricular remodelling.^{21,22}

It is important to recognise that not all of the neurohumoral systems which are activated in patients after myocardial infarction (and in heart failure) are harmful and some endogenous neurohumoral systems may be protective. The best recognised of these are the natriuretic peptides. A- and B-type natriuretic peptides are secreted by the heart when it is stressed and these peptides promote vasodilation (reducing left ventricular wall stress), stimulate renal sodium and water excretion (i.e. antagonising the retention of salt and water characterising heart failure) and inhibit pathological growth i.e. hypertrophy and fibrosis (key components of the adverse left ventricular remodelling that occurs after infarction and in heart failure).²³ The augmentation of plasma levels of endogenous natriuretic peptides can be achieved through inhibition of neutral endopeptidase, also known as neprilysin (NEP), which is the enzyme responsible for the breakdown of natriuretic peptides. Recently, in PARADIGM-HF, the addition of neprilysin inhibition to blockade of the RAAS (using sacubitril/valsartan – formerly known as LCZ696), compared with RAAS blockade alone (using the ACE inhibitor enalapril), reduced the risk of heart failure hospitalisation and death in patients with HF-REF.²⁴ These exciting findings may lead to a new approach to the treatment of heart failure, with an angiotensin receptor neprilysin inhibitor (ARNI) replacing an ACE inhibitor or ARB as one of the fundamental treatments for this condition.²⁵ We believe that the same approach may be beneficial in high-risk survivors of myocardial infarction. Recently, sacubitril/valsartan was shown to ameliorate adverse left ventricular remodelling in an experimental model of acute myocardial infarction.²⁶

The objective of the present proposal is to obtain information, which is currently not available, on the cardiac effects of sacubitril/valsartan in patients with LVSD, better characterise the neurohumoral actions of sacubitril/valsartan and gather “proof-of-concept”, mechanistic, evidence in humans to support adoption of this new treatment in patients at high risk after myocardial infarction as a result of residual LVSD. Surprisingly, there is currently limited evidence about how sacubitril/valsartan works in humans. PARADIGM-HF was a large pragmatic mortality/morbidity trial with no mechanistic sub-studies and this is also true of a ongoing trial (PARADISE-MI) in acute myocardial infarction. Moreover, both trials either used or will use an ACE inhibitor (enalapril and ramipril, respectively), rather than an ARB as the active comparator for sacubitril/valsartan; use of valsartan in our study will allow us to precisely define the effects of neprilysin inhibition. A-type (or atrial) natriuretic peptide (ANP), C-type natriuretic peptide (CNP) and adrenomedullin are substrates for neprilysin and may play a role in the action of sacubitril/valsartan but have not been measured in existing clinical trials (in part because of the instability of these peptides and unfeasibility of measuring them in multi-centre, multi-national trials). Indeed, ANP and CNP are more specific substrates for neprilysin than BNP. As has been mentioned above, cardiac fibrosis appears to be important in the process of LV remodelling in patients with asymptomatic LVSD and the development of HF-REF and is reflected in circulating biomarkers which may be influenced by sacubitril/valsartan.

1.2 Study Rationale – hypothesis

We hypothesise that administration of sacubitril/valsartan, a first in class ARNI, to patients with LVSD (LVEF ≤40%) post myocardial infarction and no evidence of heart failure will result in a greater reduction in the degree of adverse remodelling, than the current standard of care, ARBs.

2 Study Objectives

2.1 Primary objective

To investigate the potential benefit of sacubitril/valsartan compared to the current standard of care, valsartan, in attenuating adverse left ventricular remodelling in high risk asymptomatic patients post myocardial infarction as a result of residual left ventricular systolic dysfunction (i.e. a reduced LVEF without symptoms or signs of heart failure).

2.2 Secondary objectives

To provide understanding of the cardiac effects and mechanisms of action of sacubitril/valsartan in patients with LVSD. This will help understanding of the clinical benefits seen in PARADIGM-HF.

3 Endpoints

3.1 Primary Endpoints

The primary endpoint is the change in indexed left ventricular end-systolic volume (LVESVI), from baseline to 12 (+/- 3 months) months, based on cardiac magnetic resonance imaging measurements.

3.2 Secondary Endpoints

- Change in other cardiac magnetic resonance imaging-based metrics (indexed LV end-diastolic volume, LVEF, LV mass index) of LV remodelling from baseline to 12 (+/- 3 months) months.
- Changes in hsTnI from baseline to 12 (+/- 3 months) months.
- Changes in NT-proBNP from baseline to 12 (+/- 3 months) months.
- Change in patient well-being as assessed by a patient global assessment questionnaire.

3.3 Tertiary Endpoints

- Changes in biomarkers of LV remodelling (sST2, Galectin 3, TIMP-1, MMP-9, Type III Procollagen Peptide and GDF-15) from baseline to 12 (+/- 3 months) months.
- Changes in neurohormonal levels (BNP, MR-proANP, C-terminal ANP, CNP, MR-proADM, cGMP, endothelin-1, neprilysin antigen, renin and aldosterone) from baseline to 12 (+/- 3 months) months.

4 Investigational Plan

4.1 Study Design

This is a single-centre prospective, randomised, double-blind, active-comparator trial designed to evaluate the effect of sacubitril/valsartan compared to valsartan on LV remodelling post myocardial infarction. We will study patients after myocardial infarction (both ST elevation and non-ST elevation) who receive the usual standard of care (including beta-blockers and mineralocorticoid receptor antagonists) who are at high risk of developing symptomatic HF-REF. Potential study participants will have suffered an acute myocardial infarction at least 3 months prior to recruitment, have a LVEF $\leq 40\%$ as measured by transthoracic echocardiography without any symptoms of HF (NYHA ≥ 2), be tolerant of a minimum dose of ACE inhibitor/ARB (ramipril 2.5mg BD or equivalent) and be treated with a beta-blocker unless not tolerated or contraindicated. Study participants must also be haemodynamically stable, defined as systolic blood pressure (SBP) $\geq 100\text{mmHg}$.

We will recruit patients with asymptomatic LVSD identified at least 3 months after myocardial infarction to ensure resolution of “stunning” (reversible LVSD). This will distinguish our study from the PARADISE-MI trial which will enrol patients up to 7 days after acute infarction and does not require all patients to have LVSD.²⁷ We did not consider it ethical to carry out a trial like the one proposed in patients with HF-REF as sacubitril/valsartan has already been shown to be definitively superior to RAAS blockade alone in those patients.²⁴

After assessing eligibility during screening, consenting patients who meet the study inclusion and exclusion criteria will be randomised in a double blinded 1:1 fashion to sacubitril/valsartan (target dose 97mg/103mg BD) or valsartan (target dose 160mg BD) and matching placebo. All patients will require to be tolerant (determined by clinical condition, SBP, and renal function) of a minimum dose of ACE inhibitor/ARB (ramipril 2.5mg BD or equivalent –*Table 4-1*) prior to randomisation. If on a lower dose at time of first screening, patients may be rescreened after an observed period of up-titration to a dose of ramipril 2.5mg BD or equivalent in-line with current standard of care and local practice. In order to minimise the potential risk of angioedema due to overlapping ACE and NEP inhibition all patients prescribed an ACE inhibitor pre-randomisation will undergo a minimum 36-hour “washout” period following randomisation prior to first dose of study drug.

Table 4-1 Total daily doses of commonly used ACE inhibitors or ARBs corresponding to ramipril 2.5mg BD (dose level 2 of study drug)

ACE inhibitor	Dose	ARB	Dose
Captopril	100mg	Candesartan	16mg
Enalapril	10mg	Irbesartan	150mg
Lisinopril	10mg	Losartan	50mg
Perindopril	4mg	Valsartan	160mg
Trandolapril	2mg		

[figure not shown]
Three dose levels of study medication will be administered in a stepwise titration (*Table 4-2*). Study drug will be started at dose level 2 (sacubitril/valsartan 49mg/51mg BD or valsartan 80mg BD) and up-titrated after 4 weeks to dose level 3 (sacubitril/valsartan 97mg/103mg BD or valsartan 160mg BD) if tolerated as assessed by clinical review (SBP and symptomatic hypotension) and laboratory evaluation (renal function). Patients already on a higher dose equivalent of ACE-inhibitor/ARB at dose level 2 (*Table 4-1*), may start at dose level 3 at investigators discretion taking into consideration the patient's prior dose level of ACE-inhibitor/ARB and clinical condition (SBP and renal function).

A dose level 1 (sacubitril/valsartan 24mg/26mg B.D) will be available during the double-blind period of the trial should patients require down-titration but the aim is to maintain the patient on the target dose level 3 for as long a duration as possible during the trial. (*Figure 4-1 Study drug initiation and up-titration*) This dose can be also be considered at the time of randomisation with a two-step titration to target dose over visits 3 and 4 if systolic BP at visit 1 is ≥ 100 to 110mmHg. Additionally, dose level 1 should be considered as initial dose in patients with moderate renal impairment (eGFR 30-60 ml/min/1.73 m²).

Table 4-2 Study drug dose levels during treatment period

Dose Level	Sacubitril/Valsartan arm	Valsartan arm
1	24mg/26mg B.D.	40mg B.D.
2	49mg/51mg B.D.	80mg B.D.
3	97mg/103mg B.D.	160mg B.D.

Figure 4-1 Study drug initiation and up-titration

* Equivalent doses detailed in *Table 4-1*

Dose level 1 can be considered for patients with SBP ≥ 100 to 110mmHg and/or moderate renal impairment (eGFR 30-60 ml/min/1.73 m²) at time of randomisation

+ down titration from dose level 3 to dose level 2 permitted during extension of treatment times in response to COVID-19 pandemic

Following randomisation the aim should be to up-titrate patients to target study drug dose level 3 (*Table 4-2*) after 4 weeks (Visit 4). Slower up-titration will be permitted if necessary to ensure patient safety and tolerability. Patients will be allowed to stay at dose level 1 or 2 as maintenance dose however efforts should be made to maintain patients on the target dose level 3 or maximally tolerated dose level for as long a duration as possible during the trial. Adjustments to study drug dose level should be based on safety and tolerability with a focus on a) symptomatic hypotension, b) clinically significant decline in renal function and c) hyperkalaemia (*Table 4.3*).

The decision to up-titrate to the next dose level at any study visit will be made based on investigator discretion and may be made on the basis of results of the laboratory investigations (urea and electrolytes) from a previous visit or those performed in routine clinical care provided these are within 14 days of the study visit. Participants will have laboratory investigations (urea and electrolytes) performed at each study visit but may be advised to await communication from the investigator prior to taking their next study drug dose. It is anticipated that results will be available within several hours of the study visit occurring and that study participants will be contacted within a maximum of 12 hours from the time of the study visit. The investigator will make all reasonable attempts to contact participants within this time period. Based on previous results and investigator discretion, the decision to up-titrate may be delayed until the results of laboratory investigations are available in which case participants will continue on current study dose until the results are available.

Treatment guidance for management of nephrotoxicity, hyperkalaemia and hypotension are provided in section 6.8.1, 6.8.2 and 6.8.3 respectively.

Table 4-3 Safety monitoring criteria that must be met for dose up-titration

Parameter	Criteria
Blood pressure	SBP \geq 100mmHg
Renal function	eGFR \geq 30mL/min/1.73m ² or serum creatinine increase $<0.5\text{mg/dL}$ (44 $\mu\text{mol/L}$)
Serum potassium	K ⁺ $<5.5\text{mmol/L}$
AEs or symptoms	No postural symptoms or any AEs that preclude up-titration according to the investigator's judgement

Study patients will remain on the allocated study drug for a period of 12 (+/- 3months) months after which their involvement in the trial will end. In response to the covid-19 pandemic down titration from dose level 3 to dose level 2 is permitted. Following their involvement in the trial they will be converted to an ACE-inhibitor or ARB as per local guidelines at an equivalent dose to their final study drug dose level. It is anticipated that recruitment of 100 patients will take 18 months with the final patient visit occurring 12 months following this meaning a total trial duration of 30 months.

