5.2 Exclusion Criteria

- Contraindication to CMR (ferrous prosthesis, implantable cardiac device or severe claustrophobia)
- Clinical and/or radiological heart failure (NYHA≥2)
- Symptomatic hypotension and/or systolic blood pressure <100mmHg
- eGFR < 30 mL/min/1.73m² and/or serum potassium >5.2mmol/L
- Persistent/permanent atrial fibrillation
- History of AMI within last 3 months
- History of hypersensitivity or allergy to ACE-inhibitors/ARB
- History of angioedema
- Known hypersensitivity to the active study drug substances, contrast media or any of the excipients
- Obesity (where body girth exceeds MRI scanner diameter)
- Pregnancy, planning pregnancy, or breast feeding
- Inability to give informed consent or comply with study protocol
- Evidence of hepatic disease as determined by any one of the following: AST or ALT values exceeding 2 x ULN at Visit 1, history of hepatic encephalopathy, history of oesophageal varices, or history of portacaval shunt
- History of biliary cirrhosis and cholestasis
- Active treatment with cholestyramine or colestipol resins
- Active treatment with lithium or direct renin inhibitor
- Participation in another intervention study involving a drug or device within the past 90 days (co-enrolment in observational studies is permitted)

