6.5 Permitted dose adjustments and discontinuation of study treatment

Every attempt should be made to maintain patients at the target study drug dose level throughout the trial. If the patient does not tolerate the target study drug dose level the investigator can, if appropriate, adjust concomitant background medications for co-morbid conditions to rectify the situation, and if necessary down titrate to the next lower study drug dose level. Any dose-adjustment of disease-modifying background therapy, e.g. beta-blockers or MRAs is discouraged.

Down-titration of the study drug at any time will be allowed based on the safety and tolerability criteria defined in Table 4-3 and section 6.8. If down-titration is necessary, the patient should be down-titrated to the next lower dose level (Table 4-2) The patient may continue receiving the lower dose level for a recommended period of 1 to 4 weeks before re-challenging the patient with the next higher dose level. For example, a patient who encounters tolerability problems at the target dose level (dose level 3), should receive the study drug at dose level 2 for 1 to 4 weeks. Then, he/she should be re-challenged with up-titration back to dose level 3. If the tolerability issues are not alleviated despite down-titration by one dose level, the investigator may lower the study drug dose further to the next lower level for 1 to 4 weeks, up to temporary withdrawal of the study drug. Study drug should be reintroduced in those who temporarily discontinue it as soon as medically justified in

the opinion of the investigator. Again, once stable, the patient should be re-challenged with up-titration to the next higher dose level every 1 to 4 weeks in an attempt to bring back the patient gradually to the target study drug dose level (dose level 3). The investigator may choose the next dose level for down- or up-titration according to his or her judgement.

In some instances, according to the safety and tolerability criteria and the investigator's judgment, dose level 1 or 2 could be maintained if he/she considers that the patient's condition would not allow any further up-titration to the target dose of study medication (level 3). In this case it would be acceptable to maintain the patient at dose level 1 or level 2, whichever is the higher and tolerated dose level by the patient.

Any dose change must be recorded on the dosage administration record on the eCRF.

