6.8 Monitoring of potential side effects

6.8.1 Management of nephrotoxicity

Both study drugs are potentially nephrotoxic and close monitoring of renal function (serum urea, creatinine and electrolytes) for the duration of the trial will be mandatory. This will include baseline measurements along with measurements prior to and after the introduction of the study drug and after any dose change. Measurements will also be taken at regular intervals for the duration of the trial. Alert ranges for laboratory and other test abnormalities are included in Appendix 1. Additional measurements will be used if clinically indicated. All results will be reviewed in a timely manner when available and if action is required this will be expedited immediately. Each patient will have their renal function (along liver function tests) checked at the following time-points:

- Visit 1: Week 0 (pre-randomisation)
- Visit 2: Week 1 (± 3 days)
- Visit 3: Week 2 (± 3 days)
- Visit 4: Week 4 (± 3 days - pre up-titration of study drug)
- Visit 5: Week 5 (± 3 days - 1 week post up-titration of study drug)
- Visit 6: Week 14 (± 7 days)
- Visit 7: Week 26 (± 7 days)
- Visit 8: Week 39 (± 7 days)
- Visit 9: Week 52 (± 7 days)

If, at any time after randomisation, eGFR decreases by $\geq 25\%$ from baseline (or if serum creatinine concentration increases to $221\text{ }\mu\text{mol/L}$), potentially reversible cases of renal dysfunction will be sought including: non-steroidal anti-inflammatory drug

intake, antibiotics, or other nephrotoxic medications; hypovolaemia; and urinary tract infection. If felt to be appropriate, the study drug dose can be reduced and continued with regular monitoring of renal function. If a patient's eGFR decreases by $\geq 40\%$ from baseline (or if serum creatinine concentration rises above 265 $\mu\text{mol/L}$, then this is an indication to stop the study drug. Thereafter, serum creatinine assessments will have to be repeated at least weekly until levels return to acceptable values. Re-challenging with the study drug at a lower dose level will be considered if deemed clinically safe to do so.

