6.8.3 Management of hypotension

Both study drugs can have the potential side effect of symptomatic hypotension and/or postural symptoms. Prior to any dose change blood pressure will be checked and up-titration will only occur if there is no symptomatic hypotension and systolic blood pressure is ≥ 100 mmHg. If appropriate, at the investigators discretion adjustments can be made to doses of diuretic and/or concomitant antihypertensive agents to facilitate the patient's ability to tolerate target study dose.

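### The renal row of Table 4-3 joins its two limits with *or*, so a patient whose eGFR has fallen below 30 still meets the up-titration criterion if creatinine rose by less than 44 µmol/L

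*Protocol*

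**What the plan says.** Protocol section 4.1 heads Table 4-3 "Safety monitoring criteria that must be met for dose up-titration". The renal row gives eGFR at or above 30 mL/min/1.73m² "or serum creatinine increase" below 0.5 mg/dL (44 µmol/L). It does not say what the increase is measured from.

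Other parts of the protocol bear on the row:

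- **Entry.** Section 5.2 excludes "eGFR < 30 mL/min/1.73m² and/or serum potassium >5.2mmol/L".
- **Renal review (section 6.8.1).** The rule begins "If, at any time after randomisation, eGFR decreases by" and sets the mark at 25% or more from baseline, or creatinine reaching 221 µmol/L. Reversible causes are then sought, and the dose may be reduced.
- **Renal stop (section 6.8.1).** For an eGFR fall of 40% or more, or creatinine above 265 µmol/L, "then this is an indication to stop the study drug".
- **Blood pressure (section 6.8.3).** Here the protocol does state an up-titration condition: "up-titration will only occur if there is no symptomatic hypotension and systolic blood pressure is" at least 100 mmHg. This matches the blood pressure row of Table 4-3.
- **Down-titration (section 6.5).** This is allowed on the "safety and tolerability criteria defined in Table 4-3 and section 6.8".
- **Judgement (section 4.1).** Up-titration is at the investigator's discretion and depends on tolerance, including renal function. Dose adjustment is to focus on, among other things, an important decline in renal function. Dose level 1 should be considered as the starting dose at eGFR 30 to 60. A pointer to section 6.8 stands just above the table.

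**The concern.** In a list of conditions that all have to be satisfied, each stated limit would normally be expected to bind. With *or*, neither renal limit binds by itself. The eGFR limit is waived by a small creatinine rise, and the creatinine limit is waived by an eGFR of 30 or more.

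The creatinine limb changes the outcome only when eGFR is below 30. Entry requires eGFR of at least 30, so anyone below 30 on treatment has crossed that limit since joining. The sole practical effect of the *or* is therefore to admit such patients to a higher dose.

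What is at stake is patient safety during titration. Section 6.8.1 regards both drugs as potentially harmful to the kidney, and the protocol aims for dose level 3 at about week 4. Section 6.8.1 contains neither an eGFR limit of 30 nor an up-titration condition that would fill the gap.

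**Working it through.** The protocol gives no figure to reproduce; the check is of the row's logic against section 6.8.1.

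**Inputs from the protocol.** Row limits: eGFR 30, creatinine rise 44 µmol/L. Review triggers: 25% fall, or creatinine 221. Stop triggers: 40% fall, or creatinine above 265. Entry limit: eGFR 30.

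**Assumptions.** The documents name no eGFR equation. I take eGFR as proportional to creatinine to the power −k, with k from 1.0 to 1.2, so creatinine ratio = (eGFR ratio)^(−1/k). The baseline creatinine values are illustrative.

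**1. eGFR now below 30**

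A fall of less than 25% can end below 30 for any baseline from 30 up to, but not including, 30/0.75 = 40.

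Example: 34 to 28 is a fall of 1 − 28/34 = 17.6%, short of the 25% trigger. The creatinine ratio is 34/28 = 1.2143 for k = 1.0, and 1.2143^(1/1.2) = 1.1756 for k = 1.2.

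| Baseline creatinine (µmol/L) | Rise, k = 1.2 to 1.0 | Final value |
|---|---|---|
| 120 | 21.1 to 25.7 | 141.1 to 145.7 |
| 150 | 26.3 to 32.1 | 176.3 to 182.1 |
| 170 | 29.9 to 36.4 | 199.9 to 206.4 |
| 180 | 31.6 to 38.6 | 211.6 to 218.6 |

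Every rise is below 44 and every final value below 221. The row passes and no 6.8.1 trigger is reached.

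Limits of the example:

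- Rise below 44 needs baseline creatinine below 44/0.2143 = 205.3 (k = 1.0) or 44/0.1756 = 250.5 (k = 1.2).
- Final value below 221 needs baseline below 221/1.2143 = 182.0 or 221/1.1756 = 188.0. This is the tighter limit.

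The room is smaller for larger falls. Near a 25% fall the ratio is 1.3333 (k = 1.0) or 1.2709 (k = 1.2). The rise then stays below 44 only for baseline creatinine below 44/0.3333 = 132 or 44/0.2709 = 162.

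Cross-check with two assumed standard equations (MDRD and CKD-EPI 2009), both sexes, ages 50, 65 and 80: a fall from 32 to 27 gives a rise of about 20 to 31 µmol/L, and 35 to 28 about 25 to 38. All 24 combinations pass the row. In three of them, all men aged 50, final creatinine is 224 to 233 and so reaches the 221 review trigger. The other 21 reach none.

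**2. eGFR still 30 or more**

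A 40% fall leaves eGFR at 30 or above for any baseline of at least 30/0.60 = 50; for example, 0.60 × 80 = 48. The row passes on the eGFR limb whatever the creatinine rise, while section 6.8.1 indicates stopping.

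**3. Would *and* be enough?**

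It closes situation 1, because every patient below 30 then fails the row. It does not fully close situation 2. A 40% fall has a creatinine ratio of 1/0.60 = 1.6667 (k = 1.0) or 1.5306 (k = 1.2). The rise is still below 44 when baseline creatinine is below 44/0.6667 = 66.0 or 44/0.5306 = 82.9 µmol/L. A short note tied to the stop thresholds is needed as well.

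**The case against.** The *or* may be deliberate. Section 6.8.1 works mainly on change: its triggers are percentage falls in eGFR and absolute creatinine levels, and it sets no eGFR floor on treatment. The exclusion at eGFR 30 governs entry only. A patient who moves from 34 to 28 may stay on study drug with no required action, and a rule that accepts a small creatinine rise fits that approach. This shows that the row could be intended. It does not explain why a mandatory row names an eGFR limit that a small creatinine rise then waives.

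The safeguards are also real. Passing the row permits a dose increase but does not require one. Section 4.1 makes the step depend on tolerance judged by renal function, directs attention to renal decline, advises considering dose level 1 at eGFR 30 to 60 and allows slower titration. Section 6.5 lets the investigator discontinue for laboratory abnormalities. Renal function is checked again one week after up-titration (Visit 5). All of this stands as mitigation, but it works by judgement and sets no fixed limit.

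Two stronger readings should be resisted. A reader might infer that the protocol directs a dose increase in patients who ought to stop. It does not: section 6.8.1 applies throughout the period after randomisation, and Table 4-3 is printed directly below a pointer to it. Nor does every patient below eGFR 30 pass, since the row still blocks one whose creatinine rose by 44 µmol/L or more.

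**Conclusion.** The point holds and is minor. As written, the renal row does not enforce its own eGFR limit when the creatinine rise is below 44 µmol/L. For baseline eGFR of 30 to under 40, a patient can drop below 30, pass the row and reach no 6.8.1 trigger; holding the dose then rests on clinical judgement. The patient at or above eGFR 30 with a fall of 40% or more is a lesser matter: the row is out of line with section 6.8.1, but the stop rule already covers that patient.

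The logical reading and the eGFR bands (30 to under 40, and 50 or more) follow from the protocol alone. The creatinine figures rest on the assumed relation and illustrative baselines. The documents do not allow the number of patients affected to be estimated. A reader might also look for an effect on the trial's inference, but nothing here changes the sample size or the primary analysis.

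**What to change.** 1. In the renal row of Table 4-3, replace *or* with *and*, and state the reference point: eGFR at least 30 mL/min/1.73m² and creatinine increase from baseline below 44 µmol/L.
2. Add a note to the table that up-titration is not permitted while a section 6.8.1 stop threshold is met (eGFR fall of 40% or more from baseline, or creatinine above 265 µmol/L).

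The cost is a small wording change, one note and a message to site staff; no additional tests are needed. The downside is that some patients may be up-titrated later or held at a lower dose level. Study drug is routinely dispensed at Visits 1, 4, 6 and 7, so a hold at week 4 could mean an unscheduled dispensing or a wait until week 14.
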